12.4.3 Handling of remaining intercurrent events of primary estimand

Reaching the protocol established criteria for RBC transfusions will be handled using a composite strategy for the primary endpoint.

Intercurrent events stemming from discontinuation of treatment, breakthrough hemolysis events, and MAVEs, whose impact is expected to be reflected, in the endpoint are handled with a treatment policy strategy.

12.4.4 Handling of missing values not related to the intercurrent event

For the primary response definitions, RBC transfusion will qualify the participant as a non-responder, hence missing hemoglobin data following having met the criteria for RBC transfusion does not impact the primary analyses.

Missing hemoglobin data due to withdrawal from study in the event that a participant did not have a prior RBC transfusion, will be imputed based on pattern mixture models which aims to be consistent with the inclusion of hemoglobin data under the treatment policy strategy following all other intercurrent events. For participants with intermittent missing data during study follow up where reasons for missingness are assumed to be unrelated to response or compliance status, their missing data will be handled with a missing at random approach and imputed consequently. The full specification will be provided in the SAP.

12.4.5 Sensitivity analyses for primary endpoint/estimand

The sensitivity of the primary estimands with respect to the treatment of missing data described above will be evaluated using a tipping point analysis. This assessment will be detailed in the SAP.

12.4.6 Supplementary analysis

A supplementary estimand considering the use of rescue therapy (as defined in [Section 6.2.3](#)) under intercurrent event as treatment failure, for the purpose of efficacy assessment, will be performed. The supplementary estimand will have the same population, treatment of interest, summary measure as the primary estimand in [Section 2.1](#). For this analysis, transfusions will be considered treatment failures whereas discontinuations of study medication for any reason will be handled with treatment policy strategy.

12.4.7 Supportive analyses

The estimation of proportions described above will be further displayed for subgroup categories defined by previous transfusion dependence, length of time since diagnosis, prior supportive therapy (e.g. steroids, androgens etc.), age categories, sex, and baseline hemoglobin.

Other supportive analyses

Potential impact of a new wave of COVID-19 infections affecting measurements have been minimized through the measures proposed in [Section 8](#). Other impact that at this stage cannot be excluded such as withdrawal from study follow up due to infection which would require dealing with such events as additional intercurrent events. This would define additional estimands, possibly primary and secondary estimands all of which would deal with the COVID-19 related intercurrent events so that inference would still concern treatment effects in a world that is not in the midst of an extraordinary pandemic situation. The methodology for the analyses targeting these estimands and additional sensitivity analyses for cases of missing data due to the impact of COVID-19 infections will be specified in detail in an amendment to the SAP developed in the event of renewed COVID-19 infection waves. Decisions on handling of possible increases in background risks impacting study endpoints will also take into consideration relevant epidemiological information on local incidence of COVID-19 infections.

12.5 Analysis of secondary endpoints/estimands

12.5.1 Efficacy and/or Pharmacodynamic endpoint(s)

Handling of RBC transfusions will depend on the endpoint and this is described below. In the case of discontinuation of study medication, breakthrough hemolysis, or MAVEs, these are intercurrent events which are expected to be reflected in the endpoints, hence the treatment policy strategy will be applied.

The proportion of participants achieving sustained hemoglobin levels ≥ 12 g/dL in the absence of red blood cell transfusions will be evaluated by means of standardized marginal proportions.

Transfusion avoidance will be evaluated as the proportion of participants not requiring (i.e. not received and not met the criteria for administration as per [Section 8.3.2](#)) any transfusion between Day 14 and Day 168, and the estimation will be evaluated by means of standardized marginal proportions derived similarly to the estimation applied to the primary estimand.

Change from baseline in hemoglobin levels is estimated under the hypothetical situation in which participants would not have received transfusions on iptacopan treatment. This will be accomplished by the use of imputed values based on a normal distribution whose mean is restricted to a range consistent with not having received an RBC transfusion and the within visit covariance matrix will borrow from the observed within participant covariance matrix, to replace hemoglobin values following a transfusion. The model for the estimation is a repeated measures model with an unstructured covariance structure, and including visit and baseline hemoglobin levels and the interaction between visit and baseline levels. Additional covariates will be age (categorical), sex and transfusion dependency. The treatment estimates will be computed as the mean changes corresponding to the average of hemoglobin levels measured in the last 6 weeks of treatment (that is the visits occurring between Day 126 and Day 168).

Changes from baseline in scores of fatigue using the FACIT-Fatigue questionnaire will be derived from a longitudinal repeated measures model including test scores collected as all visits. The baseline is defined as the mean of levels obtained pre-treatment (Screening visit) and Day 1 value. The estimation will be an average of treatment estimates derived for visits occurring

between Day 126 and Day 168. Main effects will be transfusion dependency and interaction terms will be the same as those used to compare changes in hemoglobin.

The estimation of the change from baseline in reticulocyte counts will be derived from a longitudinal repeated measures model including data collected throughout the study and where baseline is defined as the value on Day 1. In this model, transfusion dependency, baseline covariates as well as interaction terms will be the same as for changes in hemoglobin. The estimation will use the average of model derived estimates obtained at visits occurring between Day 126 and Day 168.

The treatment effect on percent change from baseline in LDH will be assessed using a longitudinal repeated measures model of log transformed ratio to baseline based on all observations collected during follow-up. The model is the same to the model described for all continuous endpoints. Estimation will be derived based on the average of the log transformed ratio estimated between Day 126 and Day 168.

The estimation of rates of Major Adverse Vascular Events (MAVE) will be carried out using a negative binomial model. Due to the expected low frequency of occurrences, no covariates are planned to be included.

The estimation of rates of breakthrough hemolysis (BTH) will be carried out using a negative binomial model. Transfusion dependency and covariates will be included similarly as for the other endpoints.

In all estimations based on a longitudinal model, missing data will be imputed multiple times under a model that considers the reasons for missingness. The imputed datasets will be used in the estimation of the longitudinal model. For the analysis of change from baseline Hb and/or where missing data are imputed, the model comparisons will be derived using Rubin's combination rules.

12.5.2 Safety endpoints

The analysis set used for all safety analyses will be the safety set (SAF). All tables will be presented. The complete details of all safety summaries will be provided in the SAP. The following mentions safety outcomes of interest and provides a non-exhaustive description of principles to be followed in the preparation of outputs.

Safety summaries (tables, figures) include only data from the on-treatment period with the exception of baseline data which will also be summarized where appropriate (e.g., change from baseline summaries). In particular, summary tables for adverse events (AEs) will summarize only on-treatment events, with a start date during the on-treatment period (treatment-emergent AEs). In addition, a separate summary of death events including on treatment and post treatment deaths will be provided if appropriate.

The on-treatment period lasts from the date of first administration of study treatment to 7 days after the date of the last actual administration of iptacopan which covers slightly more than 5 times the estimated half-life of iptacopan.

Adverse events

All information obtained on adverse events will be displayed by participant.

The number (and percentage) of participants with treatment emergent adverse events (events started after the first dose of study medication or events present prior to start of treatment but increased in severity based on preferred term) will be summarized in the following ways:

- by primary system organ class and preferred term.
- by primary system organ class, preferred term and maximum severity.

Separate summaries will be provided for study medication related adverse events, death, serious adverse events, other significant adverse events leading to discontinuation, and adverse events leading to discontinuation of study medication, and for iptacopan tapering if this is followed prior to complete study dose discontinuation.

The number (and proportion) of participants with adverse events of special interest/related to identified and potential risks will be summarized.

A participant with multiple adverse events within a primary system organ class is only counted once towards the total of the primary system organ class.

Vital signs

Summary statistics will be provided by visit/time. Summary occurrence of abnormalities may be provided if appropriate.

12-lead ECG

[figure not shown]
PR, QRS, QT, QTcF and PP intervals will be obtained from 12-lead ECGs for each participant during the study. ECG data will be read and interpreted locally.

[figure not shown]
Categorical Analysis of QT/QTc interval data based on the number of participants meeting or exceeding predefined limits in terms of absolute QT/QTc intervals or changes from baseline will be presented. In addition, a listing of these participants will be produced.

Summary statistics will be provided by visit/time.

Clinical laboratory evaluations

Laboratory data for participants with relevant abnormalities will be listed by participant and visit/time relative to the start of study medication. Summary statistics will be provided by visit/time. Shift tables using the low/normal/high/ (low and high) classification may be provided as appropriate to compare baseline to the worst on-treatment value. Other displays using based on fold increases or decreases of interest will be provided as appropriate.

[figure not shown]

12.5.4 Patient reported outcomes

In addition to the analyses below, a comprehensive analysis of PRO will be provided as a separate PRO report and documented in a separate statistical analysis plan.

In this study, the question addressed by the analysis of PRO measurements is whether treatment with iptacopan improves patient-reported fatigue symptoms as measured by the FACIT-Fatigue and this analysis is a secondary endpoint described with the secondary endpoints/estimands. This section briefly describes supportive analyses of FACIT-Fatigue as well as supportive analyses using a secondary clinical outcome instrument.

Further, responder analyses derived from changes in FACIT-Fatigue will be performed. Response is defined as at least a 5-point improvement in the FACIT-Fatigue total score from baseline at a patient-level. Given the greater variability at the patient-level, a 5-point change is recommended as a meaningful important difference.

The above analyses will include data from participants with an evaluable baseline and at least one post baseline score. Handling of missing forms due to missed visits will follow the principles applied to all other missing data throughout the study.

[REDACTED]

Descriptive statistics and displays by visit will be produced.

[REDACTED]

[REDACTED]

12.7 Interim analyses

Safety data will be monitored by an independent DMC, and analyses to the effect of this evaluation will be performed during the course of the study with the frequency to be determined in the Charter. Access to a limited number of efficacy measurements by the DMC will be

provided solely for the purpose of evaluating benefit of treatment with iptacopan against any risk. The DMC will function under a charter to be finalized prior to the first patient screening. The Charter will include guidelines for communication concerning safety of participants between the DMC and the sponsor representative to ensure that these are in keeping with the sensitive nature of the open label trial and do not introduce bias. The analyses to be provided to the DMC will also be specified in the appendix to the Charter.

Interim reports of the safety data may be produced as mentioned in [Section 4.4](#). [REDACTED] The interim reports will not consider inferences based on efficacy.

12.8 Sample size calculation

12.8.1 Primary endpoint(s)

The sample size is calculated based on the half-width (the margin of error in the estimate) of a 2-sided 95% confidence interval for the proportion of participants reaching the status of responder (primary endpoint). The proposed sample size of 40 participants is sufficient to achieve a target absolute margin of error not larger than 0.155.

The different scenarios of observed response rate and its 95% confidence intervals are shown in [Table 12-1](#).

Table 12-1 Precision of response rate with N = 40

Sample Size	Observed Response Rate	Unadjusted 95% Confidence Interval
40	30%	(15.8%, 44.2%)
40	40%	(24.8%, 55.2%)
40	50%	(34.5%, 65.5%)
40	60%	(44.8%, 75.2%)

The lower bound of the two-sided 95% confidence interval of the response rate obtained from the primary analysis will be compared to a threshold of 15% and exceeding the threshold is sufficient for demonstration that iptacopan improves hematological response in PNH patients with hemolysis and anemia in the absence of transfusions.

For the sample size of 40 participants, given the observed proportion of responders is 40%, there is 96.4% probability that the lower bound of the 2-sided 95% confidence interval (CI) will exclude a threshold of 15%.

Derivation of the 15% threshold

The threshold of 15% is derived by indirectly estimating hemoglobin response in two studies with eculizumab: Study ALXN1210-PNH-301 ([Ultomiris CHMP Assessment Report 2019](#), [Brodsky et al 2021](#)) that included a treatment naive population and the first eculizumab pivotal study, TRIUMPH ([Hillmen et al 2006](#), [Dmytrijuk et al 2008](#)) that was conducted in a more severe population of transfusion dependent patients before the availability of eculizumab as SoC for PNH. The treatment periods for both historical studies were 26 weeks.

The patient-level hemoglobin data were not available for these historical studies, and hence direct estimation of the proportion of patients who achieved hemoglobin increases from baseline ≥ 2 g/dL in the absence of transfusions was not feasible. However, an indirect approach through simulation indicates that the probability of being a responder (defined as change of hemoglobin ≥ 2 g/dL regardless of transfusions) is 14.7% (95% CI: 5.0% - 21.1%) for ALXN1210-PNH-301 and is 4.49% (95% CI: 0.5% - 11.0%) for TRIUMPH. The difference in estimated probability of being a responder between ALXN1210-PNH-301 and TRIUMPH is likely due to the difference in populations, with the TRIUMPH population consisting of all transfusion dependent patients, while ALXN1210-PNH-301 included less severe patients due to availability of SoC.

Please note these estimates (14.7% and 4.49%) actually overestimate the hematological effect for eculizumab in the studies because the hemoglobin levels correspond to all patients at Week 26 including those who have received transfusions during treatment.

The 15% threshold is chosen to be above the estimated hemoglobin increases regardless of transfusions in both historical studies, and exceeding this threshold is sufficient for demonstration that iptacopan improves hematological response in PNH patients with hemolysis and anemia in the absence of transfusions. R[®] software was used for the calculations (R Core 2017). Further details about simulation approach will be provided in Statistical Analysis Plan.

13 Ethical considerations and administrative procedures

13.1 Regulatory and ethical compliance

This clinical study was designed and shall be implemented, executed and reported in accordance with the ICH Harmonized Tripartite Guidelines for Good Clinical Practice, with applicable local regulations (including European Directive 2001/20/EC, US CFR 21), and with the ethical principles laid down in the Declaration of Helsinki.

13.2 Responsibilities of the investigator and IRB/IEC

Before initiating a trial, the investigator/institution must obtain approval/favorable opinion from the Institutional Review Board/Independent Ethics Committee (IRB/IEC) for the trial protocol, written informed consent form, consent form updates, participant recruitment procedures (e.g., advertisements) and any other written information to be provided to participants. Prior to study start, the investigator is required to sign a protocol signature page confirming his/her agreement to conduct the study in accordance with these documents and all of the instructions and procedures found in this protocol and to give access to all relevant data and records to Novartis monitors, auditors, Novartis Quality Assurance representatives, designated agents of Novartis, IRBs/IECs, and regulatory authorities as required. If an inspection of the clinical site is requested by a regulatory authority, the investigator must inform Novartis immediately that this request has been made.

13.3 Publication of study protocol and results

The protocol will be registered in a publicly accessible database such as clinicaltrials.gov and as required in European Union Drug Regulatory Authorities Clinical Trial (EudraCT). In

In addition, after study completion and finalization of the study report the results of this trial will be submitted for publication and posted in a publicly accessible database of clinical trial results, such as the Novartis clinical trial results website and all required Health Authority websites (e.g. Clinicaltrials.gov, EudraCT etc.).

For details on the Novartis publication policy including authorship criteria, please refer to the Novartis publication policy training materials that were provided to you at the trial investigator meetings.

13.4 Quality Control and Quality Assurance

Novartis maintains a robust Quality Management System (QMS) that includes all activities involved in quality assurance and quality control, to ensure compliance with written Standard Operating Procedures as well as applicable global/local GCP regulations and ICH Guidelines.

Audits of investigator sites, vendors, and Novartis systems are performed by auditors, independent from those involved in conducting, monitoring or performing quality control of the clinical trial. The clinical audit process uses a knowledge/risk based approach.

Audits are conducted to assess GCP compliance with global and local regulatory requirements, protocols and internal SOPs, and are performed according to written Novartis processes.

14 Protocol adherence

This protocol defines the study objectives, the study procedures and the data to be collected on study participants. Additional assessments required to ensure safety of participants should be administered as deemed necessary on a case by case basis. Under no circumstances including incidental collection is an investigator allowed to collect additional data or conduct any additional procedures for any purpose involving any investigational drugs under the protocol, other than the purpose of the study. If despite this interdiction prohibition, data, information, observation would be incidentally collected, the investigator shall immediately disclose it to Novartis and not use it for any purpose other than the study, except for the appropriate monitoring on study participants.

Investigators ascertain they will apply due diligence to avoid protocol deviations. If an investigator feels a protocol deviation would improve the conduct of the study this must be considered a protocol amendment, and unless such an amendment is agreed upon by Novartis and approved by the IRB/IEC and Health Authorities, where required, it cannot be implemented.

16.1 Appendix 1: Clinically notable laboratory values

Renal alert values

Once a participant is exposed to study treatment, the following two categories of abnormal renal laboratory alert values should be assessed during the study period:

- Serum creatinine increase $\geq 25\%$ compared to baseline during normal hydration status
- New onset dipstick proteinuria $\geq 3+$

Abnormal renal event findings must be confirmed after ≥ 24 hours but ≤ 5 days after first assessment. Causes and possible interventions should be considered.

ECG alert values

- Resting heart rate sinus rhythm < 30 or a HR decrease $\geq 25\%$ or HR > 130 [bpm]
- QRS > 120 or increase $> 25\%$ compared to predose baseline [msec]
- QTcF > 500 or increase > 60 compared to predose baseline [msec]
- Ventricular tachycardia
- New complete heart block (Grade III AV block) or Mobitz II AV block

For any ECGs with participant safety concerns, two additional ECGs must be performed to confirm the safety finding.

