8.4.1 Laboratory evaluations

Unless specified in the table below, a central laboratory will be used for the analysis of the specimens collected. Details of collection, shipment, and reporting by the Laboratory is provided to the investigator in the laboratory manual.

If participants cannot visit the site for protocol specified safety lab assessments, an alternative lab (local) may be used as defined in [Table 8-7](#).

Clinically notable laboratory findings are defined in [Appendix 1](#).

Clinically significant abnormalities must be recorded as either medical history/current medical conditions or adverse events as appropriate.

Table 8-5 Laboratory tests

Test Category	Test Name
Hematology - full list	Hematocrit, total Hemoglobin, Mean corpuscular hemoglobin, Haptoglobin, Reticulocytes counts, Red blood cells (RBC) count, RBC distribution width, RBC mean corpuscular volume, White blood cell (WBC) count with differentials and Platelet count

Test Category	Test Name
Clinical Chemistry (full)	Albumin, Alkaline phosphatase, ALT, AST, Gamma-glutamyl-transferase (GGT), Lactate dehydrogenase (LDH), Calcium, Magnesium, Phosphorus, Chloride, Sodium, Potassium, eGFR, hs-C-reactive protein (hsCRP), Serum creatinine, Creatine kinase, Direct Bilirubin, Indirect Bilirubin, Total Bilirubin, Total Cholesterol, LDL, HDL, Total Protein, Triglycerides, Blood Urea Nitrogen (BUN) /Urea, Uric Acid, Amylase, Lipase, Glucose (non-fasting), Ferritin
Clinical Chemistry (abbreviated)	LDH, Albumin, ALT, AST, GGT, eGFR, hs-C-reactive protein, Serum creatinine, Direct Bilirubin, Indirect Bilirubin, Total Bilirubin, Total Protein, Blood Urea Nitrogen (BUN)/Urea, Ferritin
Urinalysis/urine dipstick assessments	Dipstick measurements for protein, bilirubin, blood, glucose, ketones, nitrites, pH, specific gravity and urobilinogen, and WBC/leukocytes will be performed at the site's local laboratory (or central lab per local requirements). If dipstick measurement results are positive (abnormal), results will be captured in the CRF. Microscopy must be assessed locally (or central lab per local requirements) following an abnormal dipstick test.
UACR Urine albumin creatinine ratio	UACR will be assessed from sample obtained during the visit (Central Laboratory analysis)
Coagulation/markers of thrombosis	Prothrombin time (PT), INR, activated partial thromboplastin time (aPTT). D-dimer and fibrinogen

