2.7.3 Laboratory data

For all safety analysis based on laboratory data, the information obtained from the central as well as local labs will be used. For summaries by visits, local lab data will be used when the corresponding central lab data are missing. For summaries on overall post-baseline data, all available data (including central and local lab data) from scheduled and unscheduled visits will be used.

Laboratory evaluations' summaries will be presented for groups of laboratory data (clinical chemistry, clinical hematology, urinalysis, UACR, coagulation/markers of thrombosis and reproductive and thyroid hormone panel).

For all continuous laboratory parameters, the absolute on-treatment laboratory values will be summarized with standard descriptive statistics (mean, median, standard deviation, minimum, maximum) by parameter, and scheduled visit/time-point. The on-treatment laboratory values will be defined as in [Section 2.7](#).

For categorical laboratory parameters and categorical urinalysis parameters, a frequency table of results will be produced by laboratory parameter, scheduled visit and time-point.

It is to be noted that for analysis on SAF, different baseline values need to be considered as mentioned in [Section 2.1.1.2](#).

For summary tables on laboratory parameters considering values, which are lower or greater than the limit of quantification:

- The values less than Lower Limit of Quantification (LLoQ) will be imputed to $0.5 \times \text{LLoQ}$ and the values greater than Upper Limit of Quantification (ULoQ) will be imputed to $1.5 \times \text{ULoQ}$.
- The number and percentage of values below the LLoQ and above the ULoQ will be presented.

For the figures, imputed values will be displayed.

Plots of arithmetic mean (SD) for all lab values will be provided. Note that displays of reproductive hormone level parameters (Testosterone, DHT, LH, FSH) will be further split by sex.

The lab abnormalities using the CTCAE grading will be reported. The version 4.03 of the CTCAE grading will be used at the time of reporting and the following reports will be provided:

- New or worsening abnormalities based on CTCAE grade (hematology, chemistry)
- Shift tables based on CTCAE grade (hematology, chemistry).

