ALP > 2 × ULN (in the absence of known bone pathology) ^a ALP >3 x ULN (if bone pathology ^a is present)	ALP > 2 × ULN (>3 x ULN if bone pathology is present)
TBL: total bilirubin ALT: alanine aminotransferase ^a concomitance between abnormal laboratory values and symptoms or disease (bone disease, Gilbert syndrome) will be established based on reported AEs or medical history with a start date prior to laboratory measurement and stop date posterior to laboratory measurement. Selection of AEs and medical History is described in Table 2-3 and provided in eCRS ^b Selection of AEs described in Table 2-3 and provided in eCRS	

When a criterion contains multiple laboratory parameters (e.g. ALT or AST > 3 × ULN), the criterion should be considered as met only if the elevation in parameters occurs on the same sample day (as evidenced by the same date that the lab samples were taken).

Table 2-3 Definition of symptoms and AEs for liver toxicities

Term in table	MedDRA term(s)
Bone pathology	HLGT = Bone disorders (excl congenital and fractures)
Symptoms:	
Severe Fatigue ⁽¹⁾	PT = Fatigue
Abdominal pain right upper quadrant	PT = Abdominal pain upper
Nausea	PT = Nausea
Vomiting	PT = Vomiting
General malaise	PT = Malaise
Rash with eosinophilia	PT = Drug reaction with eosinophilia and systemic symptoms
Gilbert syndrome	PT = Gilbert's syndrome
Jaundice	PT = Jaundice PT = Jaundice cholestatic
AEs indicative of liver toxicity	
Hepatic failure	HLT = Hepatic failure and associated disorders
Hepatic fibrosis and cirrhosis	HLT = Hepatic fibrosis and cirrhosis PT = Hepatic cirrhosis
Non-infectious hepatitis	PT = Hepatitis PT = Hepatitis acute PT = Hepatitis toxic PT = Hepatitis fulminant PT = Hepatitis chronic active PT = Hepatitis chronic persistent
Liver neoplasm	HLGT = Hepatobiliary neoplasms

HLT: High Level Term

HLGT: High Level Group Term

MedDRA codes listed above are based on version 23.1 The list will be updated for each MedDRA version change and will be included in the eCRS. eCRS will be the reference for analyses.

(1) presence of Fatigue term with severity ≥ "Severe"

Renal alert values will be summarized where renal alert values are identified as:

- Serum creatinine increase ≥ 25% compared to baseline during normal hydration status
- New onset dipstick proteinuria ≥ 3+

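### SAP 2.7.3 does not separate confirmed from transient renal alerts, and abnormal-only capture of dipstick results leaves the number tested and new onset uncertain

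*Protocol*

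**What the plan says.** Protocol Appendix 1 (16.1) names two renal alert categories: a creatinine rise of at least 25% over baseline during normal hydration, and new-onset dipstick protein of 3+ or more. It then adds a retest rule: "Abnormal renal event findings must be confirmed after" at least 24 hours, and no later than 5 days, from the first assessment.

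SAP 2.7.3 carries over the categories: "Renal alert values will be summarized where renal alert values are identified as" the same two items, including "Serum creatinine increase ≥ 25% compared to baseline during normal hydration status". It does not mention the repeat. The general rules of that section take in every value: "For summaries on overall post-baseline data, all available data (including central and local lab data) from scheduled and unscheduled visits will be used". For selected parameters, abnormalities at any on-treatment time-point are summarised.

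On data capture, the urinalysis row of Protocol Table 8-5 has dipsticks read at the site's local laboratory, or centrally where local requirements call for it, and says "If dipstick measurement results are positive (abnormal), results will be captured in the CRF". Table 8-1 marks urinalysis with an X, the code for an assessment recorded in the clinical database. SAP 2.7.3 plans by-visit tables from these data: "For categorical laboratory parameters and categorical urinalysis parameters, a frequency table of results will be produced by laboratory parameter, scheduled visit and time-point".

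Safety summaries use the Safety Set unless stated otherwise (SAP 2.7).

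**The concern.** A 25% rise in creatinine can come from ordinary within-person variation, more easily when many visits are each compared with one baseline value. The repeat in Appendix 1 is what separates a lasting change from a passing one. If the report shows only threshold crossings, the reader cannot tell how many alerts persisted, how many resolved on retest and how many were never retested. With no control arm, no background rate is available for comparison.

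The dipstick question is one of data capture. A by-visit frequency table needs the number tested. New onset needs a known baseline. A failed confirmation needs the negative retest on record. If only abnormal results reach the database, none of the three can be established from the results.

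The hydration condition has a similar gap. Tables 8-1, 8-4 and 8-5 show no hydration item, and the SAP gives no rule for applying the condition.

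**Working it through.** The plan states no renal alert rate, so there is no figure to reproduce. The check compares the texts and adds an illustration of size.

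**1. Retest rule.** Appendix 1 has two thresholds plus a repeat at 24 hours to 5 days. SAP 2.7.3 has the same two thresholds, no repeat, and all scheduled and unscheduled values. As written, one value at or over the threshold is enough to be summarised as an alert. Every confirmed alert is also an alert, so the count without confirmation is at least as large as the confirmed count.

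**2. Size for creatinine (illustration).**

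Inputs from the documents:
- 40 participants.
- An alert at a ratio to baseline of 1.25 or more.
- One baseline value, the last at or before Day 1 (SAP 2.1.1.2).
- 11 post-Day 1 core visits, because creatinine is in both chemistry panels: 3 full (Days 56, 112, 168) plus 8 abbreviated (Days 7, 14, 28, 42, 84, 126, 140, 154).

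Assumed, not in the documents: within-person CV of 5% to 10%, log-normal variation, independent errors (including the retest), and no true change.

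Let σ = √ln(1 + CV²) and let b be the log-scale error in the baseline value, b ~ N(0, σ²). At one visit, p(b) = 1 − Φ((ln 1.25 + b)/σ). Averaging over b:
- at least one alert: E[1 − (1 − p(b))¹¹]
- at least one confirmed alert: E[1 − (1 − p(b)²)¹¹]

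| CV | Any alert | of 40 | Confirmed | of 40 |
|---|---|---|---|---|
| 5% | 0.73% | 0.3 | 0.037% | 0.015 |
| 7.5% | 11.4% | 4.6 | 2.0% | 0.8 |
| 10% | 28.4% | 11.4 | 8.2% | 3.3 |

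The six extension visits bring the maximum to 17 per participant. Replacing 11 by 17 gives 0.4 against 0.02 of 40 at CV 5%, and 13.8 against 4.2 at CV 10%. The core report will hold fewer than 17 visits for later enrolees, so 11 is the better basis.

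**3. Dipstick capture.** Table 8-1 schedules urinalysis at Screening, Day 1 and six later core visits (Days 28, 56, 84, 112, 140, 168). If results enter the CRF when abnormal, an empty field can mean either negative or not done. This has three consequences:
- By-visit percentages: the number tested is not known from the results.
- New onset: a missing baseline looks like a negative one.
- Confirmation: a negative retest looks like no retest.

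The Safety Set is a defined participant-level denominator, but it includes anyone not tested. Take two participants with alerts as an example: 2/40 = 5.0%, 2/38 tested = 5.3%, 2/32 tested = 6.25%. Using all 40 therefore tends to understate the dipstick rate.

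**4. What is not affected.** Creatinine comes from the central laboratory by default and is reported whether normal or not. UACR is measured centrally. Neither falls under the abnormal-only rule.

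**The case against.** The strongest reply is that the documents do not conflict. Appendix 1 calls the two thresholds the alert values. The confirmation sentence stands apart and is followed by advice to consider causes and interventions, so it can be read as a step for the site. The SAP then summarises exactly what the protocol calls alerts. It does the same elsewhere: the protocol asks for two further ECGs to confirm an ECG finding and for repeat liver tests, yet SAP 2.7.3.1 and Table 2-2 count without confirmation. Counting every alert is a sensitive convention for safety, and unscheduled retest values remain in the data.

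Much of this stands. A reader might infer that the SAP chose to count single unconfirmed values; in fact it is silent and neither adopts nor rejects confirmation. Even on the site-step reading, though, the report would not show which alerts were confirmed, although the protocol requires the repeat that would show it.

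On dipsticks, the CRF is not among the documents. Table 8-5 does not say that results are captured only if abnormal, nor that test completion goes unrecorded, and the X in Table 8-1 points the other way. That is fair, and it is why the tables need reconciling; the gap is not proved.

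Other renal data are also planned: UACR at Day 1, Day 84 and Day 168 in the core period, by-visit creatinine summaries, CTCAE shift tables, and adverse event reporting of clinically significant abnormalities. They reduce the stakes. UACR covers two post-baseline core visits against six for urinalysis, so it does not fully replace the dipstick. On hydration, urea and specific gravity are collected as indirect indicators, but no rule uses them.

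**Conclusion.** The point holds in limited form. SAP 2.7.3 does not separate confirmed from transient renal alerts although the protocol requires a confirming repeat. The direction is certain. The size is not: over the core period it runs from negligible (0.3 of 40 at CV 5%) to material (11.4 of 40 at CV 10%, against 3.3 confirmed), on an assumed CV and independent errors. If transient changes last for days, the repeat would remove fewer alerts than shown. Local values mixed with a central baseline would add variation that the calculation leaves out.

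For dipstick urinalysis only, Tables 8-1 and 8-5 do not fit together. On results alone, by-visit percentages, new onset and failed confirmation cannot be relied on.

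Two stronger readings should be resisted. One is that the renal alert rate as a whole is inflated: the documents give neither a rate nor a variability figure, and over the Safety Set abnormal-only capture would tend to lower the dipstick rate. The other is that the renal summary has no valid denominator: creatinine and UACR are unaffected, and the Safety Set is the stated denominator. The table is descriptive, with no test or decision rule attached.

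**What to change.** - **SAP 2.7.3:** for each renal criterion report three lines: any alert; confirmed alert (a repeat in the Appendix 1 window still meets the threshold); and alert not retested.
- **Hydration:** footnote the creatinine criterion to say that hydration status is not collected as a data item and is not applied in the programmed definition.
- **Tables 8-1 and 8-5:** reconcile them so that each scheduled dipstick is recorded as done or not done, with its result, including negative. Retests need the same record.
- **New-onset proteinuria:** use participants with a baseline dipstick as the denominator, and show how many lack one.

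For creatinine this needs no new data, only SAP wording and extra lines in a descriptive table. The dipstick change costs more: additional CRF entry and, if made mid-study, back-entry from source at the sites.
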